13.3 Stratification Factors

Eligible patients will be randomized on a 1:1 ratio, with randomization stratified by presence or absence of liver involvement and LDH (< 2 times the ULN versus ≥ 2 times the upper limit of normal), to one of the two treatment arms.

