13 STATISTICAL CONSIDERATIONS

13.1 Study Design/Endpoints

The prognosis for patients with metastatic disease is poor, but this is an encouraging time and there are many agents which could be examined. Therefore, 2 investigational treatment strategies will be assessed in this trial.

A total of 80 patients with advanced stage melanoma will be randomized to either trametinib plus GSK2141795 or trametinib alone (40 evaluable patients per arm). The primary endpoint of this study is time to progression (PFS) defined from the date of randomization to the date of documented progression or death. Patients will be assessed for progression every 8 weeks. PFS will be calculated as time from randomization to the earlier date of objective disease progression per RECIST criteria or death due to any cause in the absence of progression; patients who have not progressed or died at the time of analysis will be censored at the time of their latest evaluable objective tumor assessment. It is estimated that median PFS for the trametinib arm is 16 weeks based upon the results of CTEP8443 as presented at the 2013 ASCO Annual Meeting which demonstrated a median PFS of 15.9 weeks with selumetinib (n = 47, 95% CI, 8.4 – 23.1 weeks). With 80 patients and with 76 progression events, the probability is 80% that the study will detect a treatment difference at a one-sided 5% significance level, if the true hazard ratio is 0.56.

Overall survival will be analyzed using the same methods as used for PSF. Overall survival will be calculated as time from randomization to death due to any cause; patients who have not died at the time of analysis will be censored based on the last recorded date on which the subject was known to be alive.

This is based on the assumption that the accrual period will be approximately 26 months, the follow up period will be 12 months, and the median PFS for trametinib alone is 16 weeks. It is anticipated that 3 patients per month will be accrued to this study and hence the study accrual will be completed in approximately two years and the trial will be completed in approximately three years.

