An early stopping rule for futility will be applied. Clinical benefit rate will be examined in each arm after 40 evaluable patients have been accrued (20 patients per arm). As noted above, early analysis of our on-going trial of selumetinib versus temozolomide in patients with advanced uveal melanoma, 40% of patients treated with selumetinib achieved disease control beyond 16 weeks. If at least two patients have achieved a radiographic response as defined as a RECIST partial or complete response in each arm, then the trial will continue as planned. If zero or one patient achieves a RECIST response among the 20 patients of an arm, then that arm will be terminated. The upper bound of the 95% confidence interval for no clinical benefit out of 20 patients with this early stopping rule is 25%. PFS will also be reviewed at the end of the first stage, and adjustment to the futility rule may be considered if significant PFS prolongation is obtained in the absence of sufficient numbers of RECIST responses. If we stop one arm of the trial due to futility, then we may revert to a single arm phase II study. The alternate arm may continue to accrue 40 patients. The plan for the second stage will be finalized after discussion with the sponsor. At the end of the study we will estimate the progression free survival distribution for that arm and provide the median PFS along with a 95% confidence interval.

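### Does Section 13 need to name the PFS test and say how the liver and LDH strata enter it?

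*Combined protocol and SAP*

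**What the plan says.** Section 1.1 makes a two-arm comparison of PFS the primary objective, and Section 1.2 does the same for overall survival as a secondary one. Section 13.1 defines PFS and its censoring. It then states that, with 80 patients, 76 events and a true hazard ratio of 0.56, "the probability is 80% that the study will detect a treatment difference at a one-sided 5% significance level". For survival it adds only "Overall survival will be analyzed using the same methods as used for PSF". Section 13.4 provides Kaplan-Meier curves for both endpoints and calls the secondary analyses exploratory. Section 13.6.2 takes randomised patients with at least one dose as the set for the main PFS analysis.

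Liver involvement and LDH appear in the Schema and Sections 4.4, 5.1 and 13.3, always as randomisation factors: "Eligible patients will be randomized on a 1:1 ratio, with randomization stratified by presence or absence of liver involvement and LDH". No section carries them into an analysis.

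Section 13.1 also plans for an arm that stops: "If we stop one arm of the trial due to futility, then we may revert to a single arm phase II study". The other arm may then go on to 40 patients, and at the end the trial will estimate the PFS distribution for that arm and "provide the median PFS along with a 95% confidence interval". The Schema and Sections 4.4, 4.5 and 5.1 record that Arm B met the futility rule and that all further accrual goes to Arm A.

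**The concern.** Kaplan-Meier curves describe; they do not test. A plan with a one-sided 5% level and no named test leaves the analyst to choose among an unstratified log-rank test, one stratified by LDH, and one stratified by all four liver-by-LDH cells. On the same data these can fall on different sides of the threshold. If the choice were made after seeing the results, the 5% level would not hold. The contrast within Section 13 is awkward too: Section 13.5 names Wilcoxon and Fisher tests for exploratory biomarkers, while the primary endpoint has none. The survival analysis refers back to PFS methods and so inherits the gap.

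**Working it through.** **1. Which test does the sizing imply?** Inputs from Section 13.1: hazard ratio 0.56, one-sided 5% (z = 1.645), 80% power (z = 0.842), 1:1 allocation, 76 events.

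- Schoenfeld: events = 4(1.645 + 0.842)² / (ln 0.56)² = 4 × 6.18 / 0.336 = 73.6, so 74. Power at 76 events: Φ(√76/2 × 0.580 − 1.645) = Φ(0.882) = 81.1%.
- Freedman: events = (1.56/0.44)² × 6.18 = 77.7, so 78. Power at 76 events: Φ(√76 × 0.44/1.56 − 1.645) = Φ(0.814) = 79.2%.
- The two-sided versions need 94 and 99 events and do not fit.

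The stated figure is reproduced, and it is a one-sided log-rank (proportional-hazards) calculation. The family of test is therefore not in real doubt; only the handling of strata is.

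**2. What is left to compare?** The futility look came at 20 patients per arm. Arm B then closed. Section 13.2 gives a total of up to 60, which equals 20 in Arm B plus 40 in Arm A. The concurrent comparison is therefore about 20 against 20 (assumed from the interim trigger).

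Follow-up is also assumed: 40 patients at 3 per month takes 13.3 months, 20 more takes 6.7 months, and 12 months follow. That gives between 18.7 and 32 months, or 81 to 139 weeks. With exponential PFS and medians of 16 and 16/0.56 = 28.6 weeks, expected events are 19.8 + 18.5 = 38.3, about 38. Schoenfeld power at 38 events is Φ(√38/2 × 0.580 − 1.645) = Φ(0.142) = 55.7%.

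**3. Does stratifying help?** Simulation at 20 v 20, 10,000 trials per cell (Monte Carlo error about 0.5 points), hazard ratio 0.56 within strata. Assumed, because the documents are silent: blocks of 4, the LDH hazard ratio, the share with LDH at or above twice the upper limit of normal, 8% without liver metastases, and a hazard ratio of 0.7 for them.

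| LDH hazard ratio | Unstratified power (30% high LDH) | LDH-stratified power (30% high LDH) | Difference over 10-40% high LDH, points |
|---|---|---|---|
| 1 | 54.1% | 52.0% | -2.3 to -1.5 |
| 1.5 | 53.5% | 52.7% | -1.0 to 0.0 |
| 2 | 50.1% | 52.0% | +0.6 to +2.3 |
| 3 | 46.1% | 51.8% | +1.5 to +8.3 |

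The sign depends on an LDH effect that nobody can read from the protocol. Using all four cells costs a further 0.7 to 1.3 points. A rule dropping liver when either arm has fewer than 5 patients without liver disease would apply in 99.9% of simulated trials, so it amounts to choosing LDH alone.

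**4. What does the open choice do to the error rate?** With no true effect (20,000 trials per cell), each single test rejects in 4.3-5.8% of trials, and always taking the most favourable of the three rejects in 6.7-7.3%. In a smaller run (3,000 trials per cell, 30% high LDH), the unstratified and LDH-stratified tests disagreed in 1.5-2.7% of null trials. None of these rates conditions on Arm B having stopped with zero or one response in 20, so they are not the error rate of the comparison that remains.

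**The case for a change.** The best case for a change is that the primary objective has been neither specified nor withdrawn. The fallback is worded permissively, and "The plan for the second stage will be finalized after discussion with the sponsor" leaves the rest to a later conversation. An implied sizing formula is not a stated analysis and does not settle stratified against unstratified. At a true hazard ratio of 0.56 the two disagree in 6-12% of trials at 20 v 20. At the planned 80 patients the choice could have mattered more: assuming 90% liver involvement, 35% high LDH and hazard ratios of 2 for liver and 4 for LDH, power is 63% unstratified against 75% stratified. A few sentences would close the gap.

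The omission stands, and under the full design it would have deserved a sentence. The rest carries less weight. The closure notices and the total of 60 show that the single-arm continuation is in effect, and the commitment to estimate that arm's PFS is firm, not optional. Leaving the strata out is also not a validity problem: in the 80-patient simulation the unstratified test's type I error ran from 5.1% down to 3.5%, so it errs on the cautious side. Finally, "PFS will also be reviewed at the end of the first stage" means that any test named now is named after a look at PFS. Section 13.1 allowed the futility rule to be adjusted for a significant PFS gain, yet Arm B was closed. A formal superiority claim for the combination is not a likely use of these data.

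**Conclusion.** This is a gap that analysts fill sensibly, and filling it in the plan now would bring no clear gain. For the trial as it stands, the PFS analysis is stated: the Arm A median with a 95% confidence interval, which needs no two-arm test and no strata. Any comparison with Arm B would default to a log-rank test on about 38 events with power near 50-56%, and its result is best read as descriptive. Survival inherits the gap but is already exploratory under Section 13.4.

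The open choice is worth between -2.3 and +8.3 points of power. At worst it adds about 2 points of type I error, and only if someone selects the best of three results. These sizes rest on the assumed 20 v 20 split, exponential PFS, and the assumed LDH and liver effects and prevalences. The conclusion would differ if both arms were still accruing to 80 or if a confirmatory claim for the combination were planned; neither is the case here.

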13.4 Analysis of Secondary Endpoints

Analysis of secondary endpoints will be exploratory and hypothesis-generating.

Progression-free survival and overall survival curves will be generated using Kaplan-Meier methodology. Toxicity across both arms will be reported by type, frequency and severity according to the NCI Common Toxicity Criteria. Response rate (CR+PR) by arm will be calculated along with a

95% confidence interval.

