1.2 Secondary Objectives

- To compare overall survival between those treated with trametinib alone and those treated with the combination of trametinib and GSK2141795
- To compare the overall response rate between those treated with trametinib alone and those treated with the combination of trametinib and GSK2141795
- To compare the safety and toxicity between those treated with trametinib alone and those treated with the combination of trametinib and GSK2141795

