5 TREATMENT PLAN

5.1 Agent Administration

Treatment will be administered on an outpatient basis. Reported adverse events and potential risks are described in [Section 7](#). Appropriate dose modifications are described in [Section 6](#). No investigational or commercial agents or therapies other than those described [below](#) may be administered with the intent to treat the patient's malignancy.

Eligible patients will be randomized on a 1:1 ratio, with randomization stratified by presence or absence of liver involvement and LDH (<2 times ULN vs ≥ 2 times the upper limit of normal), to one of the two treatment arms:

1. Arm A (Trametinib): Experimental Arm A will explore the activity of MEK inhibition

using trametinib in advanced UM. Patients randomized to this arm will receive trametinib 2 mg PO QD in 4 week cycles.

2. Arm B (Trametinib + GSK2141795): Experimental Arm B will explore the activity of combined MEK + AKT inhibition in advanced UM. Patients randomized to this arm will receive trametinib 1.5 mg PO QD in combination with GSK2141795 50 mg PO QD in 4 week cycles.

Patients will remain on their initially assigned treatment arm until the sooner of (i) disease progression (primary outcome measure) or (ii) the development of unacceptable toxicity that is not manageable with dose reduction. At that point, patients initially randomized to Arm A that experienced objective disease progression will be given the option of receiving additional experimental therapy with trametinib 1.5 mg QD and GSK2141795 50 mg QD.

The option of crossover will not be available to patients who are taken off treatment due to the development of unacceptable toxicity that is not manageable with dose reduction. Tumor response assessments and progression-free survival following cross-over will be recorded, but, for the purposes of the primary endpoint of progression-free survival after first randomization, these patients will be counted as a progression-event. Clinical outcome following cross-over will be followed and reported in a descriptive fashion.

Patients randomized to Arm A will be eligible for crossover if they meet the eligibility criteria outlined in [Section 3.0](#).

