- k: Serum will be collected from patients as outlined in [Section 9](#) prior to treatment, at the beginning of each cycle, and at the off-study visit and subsequently stored for future correlative studies. The samples drawn prior to treatment can be drawn on C1W1 prior to initiation of study drug.
- l: Two 10 cc lavender top tube (EDTA) will be collected prior to treatment, at the beginning of each cycle, and at the End of Treatment visit. The samples drawn prior to treatment can be drawn on C1W1 prior to initiation of study drug.
- m: Cycle 4+ will be conducted as indicated for cycle 3.
- n: End of Treatment Visit performed 4 weeks from last treatment. Patients will be contacted or evaluated every 12 weeks (+/- 1 week) for survival assessment after End of Treatment visit or last date of follow up. In the event that the patient's health deteriorates such that the follow-up visit is not feasible, a note will be placed in the subject's medical record documenting the situation. This will not be considered a protocol violation. In addition, the last treatment visit can be considered the End of Treatment visit if the patient is unable to return, a note will be placed in the subject's medical record documenting this situation.
- o: Test can be performed locally.

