13.5 Analysis of Exploratory Endpoints

For patients who progress on trametinib and crossover to the combination arm clinical outcomes will be summarized. Response rate (CR+PR) will be estimated along with progression-free and overall survival from the start of combination therapy. Toxicity for the crossover patients will be reported by type, frequency and severity according to the NCI Common Toxicity Criteria.

Clinical response will be associated with Gnaq/11 mutational status using Wilcoxon rank sum test. An additional exploratory objective is to assess whether circulating tumor DNA can be detected. If so, these numeric data will be summarized by clinical response.

Using the 30 or more paired tumor biopsies collected on this study, associations between suppression specifically of p-ERK, AKT, Cyclin-D1, and response to treatment will be assessed using Fisher's exact test. Baseline and post-treatment status as well as changes will be reported. Assessment of apoptosis in the paired samples will be performed by caspase3 cleavage; changes will be assessed by a Wilcoxon signed rank test. These correlative studies will be considered exploratory in nature.

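### Section 13.4 reports toxicity as crude frequency over an outcome-dependent window, so the between-arm comparison in 1.2 mixes toxicity with time on drug; a common fixed window would separate them at little cost.

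*Combined protocol and SAP*

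**What the plan says.** The secondary objective in 1.2 is comparative: "To compare the safety and toxicity between those treated with trametinib alone and those treated with the combination of trametinib and GSK2141795". Section 13.4 gives the method: "Toxicity across both arms will be reported by type, frequency and severity according to the NCI Common Toxicity Criteria". It prefaces all secondary analyses with "Analysis of secondary endpoints will be exploratory and hypothesis-generating" and names no test for toxicity. Sections 13.4, 13.5 and 13.6.1 contain no exposure adjustment, person-time rate, fixed window or time-to-first-event summary.

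The length of observation is set elsewhere. Section 5.1 says "Patients will remain on their initially assigned treatment arm until the sooner of (i) disease progression" or unmanageable toxicity. The study calendar (section 10) has AEs evaluated throughout treatment and again at a closing visit: "End of Treatment Visit performed 4 weeks from last treatment". Section 5.4 also gives 4 weeks of follow-up, and the expedited-reporting table in 7.3.3 uses 30 days. Section 13.6.1 says when a patient becomes evaluable for toxicity but not when that ends.

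On crossover, 13.5 adds a separate summary: "Toxicity for the crossover patients will be reported by type, frequency and severity". No section says whether those events also count under Arm A.

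Sections 4.4 and 5.1 record that Arm B met the futility rule as of 11/06/2015, that the remaining patients go to Arm A, and that Arm B and crossover enrolment are closed. Section 5.1 also requires all patients to be off treatment by March 31, 2017. The objective in 1.2 and the method in 13.4 still describe two arms.

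**The concern.** A crude frequency answers how many patients had an event while they were being watched. When the watching stops soon after progression, and progression is the primary endpoint, efficacy feeds directly into the harm table. A combination that delayed progression would look more toxic partly because its patients were observed longer. A combination that shortened time on drug would look safer for the same reason. Events that start late or accumulate are the most exposed; section 2.2.1.3 gives a median onset of 63 days for trametinib cardiomyopathy. At stake is how the added toxicity of the AKT inhibitor is read, which is one of the three secondary comparisons.

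**Working it through.** **Inputs.** Median PFS on trametinib 16 weeks, 80 patients, 76 events, one-sided 5%, 80% power, "if the true hazard ratio is 0.56", 26 months accrual and 12 months follow-up (all 13.1); 4-week tail (5.4 and 10); 30-day tail (7.3.3). Assumptions not in the documents: PFS is exponential, treatment time equals PFS, and the AE hazard is constant unless stated.

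**1. The plan's own figure.** Power = Φ(√(76 × 0.25) × (−ln 0.56) − 1.645) = Φ(2.527 − 1.645) = 81.1%, against the stated 80%. It reproduces.

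**2. Windows under the alternative.** λ_A = ln 2 / 16 = 0.0433 per week, mean 23.1 weeks. λ_B = 0.56 × λ_A = 0.0243, mean 41.2 weeks. The treatment ratio is 1/0.56 = 1.79, or 1.65 if follow-up is limited to 12–38 months. With the 4-week tail the windows are 27.1 and 45.2 weeks, ratio 1.67.

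**3. Crude incidence at an equal constant AE hazard h.** Incidence = 1 − exp(−4h) × λ/(λ + h). Choose h to give the Arm A value, then apply it to Arm B:

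| Arm A | Arm B | False excess (points) |
|---|---|---|
| 10% | 15.7% | 5.7 |
| 20% | 29.5% | 9.5 |
| 30% | 41.8% | 11.8 |
| 50% | 62.6% | 12.6 |

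**4. Dependence on the true hazard ratio** (Arm A at 30%). Arm B shows 41.8% at 0.56, 36.9% at 0.70, 34.2% at 0.80, 30.0% at 1.0 and 26.9% at 1.2.

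**5. Early events.** If the hazard exists only in the first L weeks of treatment, incidence = h/(h + λ) × (1 − exp(−(h + λ)L)). For L = 4 to 8, Arm A at 30% gives Arm B 31.1% to 32.1%; Arm A at 50% gives 51.6% to 53.2%. The excess is 1 to 3 points.

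**6. Crossover.** It comes at progression, so closing Arm A's window there removes at most the tail. If every Arm A patient lost it, the window ratio would be 45.2/23.1 = 1.96; if half did, 45.2/25.1 = 1.80. The documents give no crossover rate. Leaving the window open pushes the other way, because combination events would be counted under trametinib alone.

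**7. Do the remedies work?** Take an equal hazard giving 20% by 16 weeks (h = −ln 0.8 / 16 = 0.0139) and a 30-day tail.
- Crude incidence over the whole window: 29% v 40%.
- Incidence through week 8: 10.2% v 10.4%. The common window removes almost all of the bias.
- An exposure-adjusted rate gives a ratio of 1.0 here, but not for front-loaded events. Suppose 30% of patients in both arms have the event in the first 4 weeks (h = −ln 0.7 / 4 = 0.0892) and none later. Person-time at risk = 0.3/h + 0.7 × (1/λ + 30/7 − 4) = 19.7 v 32.4 weeks. The rate ratio B/A is 19.7/32.4 = 0.61, although incidence is identical.

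**The case against.** The strongest reply is that the scenario is hypothetical. The hazard ratio of 0.56 is the alternative used for power, and Arm B has since closed for futility. Treatment also stops for toxicity and, under 5.3, may continue past progression, so treatment time is not PFS. Section 13.4 is labelled exploratory and names no test, and incidence over actual treatment is a legitimate description of patient risk. The common toxicities with a stated onset are mostly early: skin events at a median of 15 days (2.2.1.3), and most GSK2141795 diarrhea in the first 3 to 4 weeks (5.1.3).

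Most of this stands, and it limits the size and severity of the point. It does not remove the point. Arm B patients were treated and 1.2 still promises a comparison. Arm A went on accruing, its later patients could not cross over, and the March 2017 stop truncates late entrants. Unequal windows therefore remain possible in either direction.

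Three stronger readings are tempting, and the documents do not support them:
- **That the plan expects Arm B to be treated 1.8 times as long.** No section states an expected treatment duration for Arm B. The ratio follows only from the powering alternative plus the assumptions above, and for the AE window it is about 1.67.
- **That Arm A's AE window closes at crossover.** That is an inference from the separate summary in 13.5; the plan is silent.
- **That exposure-adjusted rates should replace crude frequency as the main comparison.** Step 7 shows they can make the combination look about 39% less toxic when early incidence is equal.

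**Conclusion.** The gap is real and modest. A comparative safety objective is served only by crude frequency over a window whose length depends on outcome and whose end, particularly at crossover, is undefined. The false excess of about 6 to 13 points requires a hazard ratio of 0.56, exponential treatment time equal to PFS and a constant AE hazard. It shrinks to 1 to 3 points for events confined to the first 4 to 8 weeks, vanishes at a hazard ratio of 1.0 and reverses above it. The direction and size in the actual data cannot be known from the documents, because the realised exposure by arm is not given. This is a cheap improvement of low severity, given the exploratory status of 13.4.

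**What to change.** In 13.4, for patients randomised while both arms were open:

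1. Base the between-arm comparison on incidence of each AE type, and of any grade 3 or higher AE, in a common fixed window from first dose through week 8, before the first scheduled scan leads to discontinuation.
2. State when each arm's AE window closes. For the analysis, end Arm A's AE time and events at the first crossover dose.
3. Report treatment exposure by arm.
4. Add exposure-adjusted first-event rates as a supplement for later-onset events, with the same at-risk definition in both arms. Do not use them as the main measure for early-onset AEs.
5. Keep crude frequencies as description.

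The cost is some SAP wording and two or three extra table columns, from dosing and AE dates already collected. The week-8 window (56 days) misses late events; the 63-day median onset of cardiomyopathy falls outside it, which is why the supplementary rate is needed. The window is also not perfectly complete: under the exponential model 71% of Arm A and 82% of Arm B would still be on treatment at week 8. The post-treatment follow-up covers most of that gap, as the 10.2% v 10.4% result shows.
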